### ***Experimental setup***

This research is a 2-arm, parallel, open label, non-blinded randomized controlled trial comprised of four independent but interrelated studies with the same participants. The familiarization phase, enrollment verification, obtaining verbal consent to participate, and gathering screening information will be done via phone interview. After screening participants, the Medical and Demographic Questionnaire will be administered. The participant will be e-mailed a link to complete the following surveys/questionnaires: Medical and Demographic questionnaire, Waterloo Footedness Questionnaire to determine their dominant lower extremity, and The Survey of Phantom Limb Awareness and Control that is a commonly used questionnaire regarding phantom phenomena. The participant can use a smartphone, iPad or computer to answer these surveys/questionnaires. Completion of the surveys/questionnaires at the home will respect COVID-19 restrictions by diminishing time spent with the researcher. If the participant is not able to complete the surveys/questionnaires prior to their first scheduled visit, they will be given the opportunity to do at WinPO prior to the physical function evaluation. At the conclusion of the phone interview, the researcher will randomly assign participants to the control or exercise groups. Participants in both groups will then be scheduled for an in-person baseline visit and an in-person follow up visit at WinPO for data collection. The baseline visit will begin with review of expectations and the participant will sign informed consent. All information gathered at the phone interview will be reviewed for accuracy. If the participant has not answered the questionnaires/surveys prior to their baseline visit, they will be provided an iPad to complete the Medical and Demographic Questionnaire, Waterloo Footedness Questionnaire, and The Survey of Phantom Limb Awareness and Control. The baseline testing session will be entirely the same for participants of both groups. During this session, the researcher will assess participants based on their anthropometric variables (i.e. height, weight, body mass index), the morphology of the residual limb (i.e. length, circumference, and volume),—prostheses embodiment as measured by TAPES-R and PEmbS-LLA, and functional abilities as measured by targeted phantom motor execution and FSST, while recording their muscle activities and plantar foot loads. After completion of the baseline testing, the researcher will contact [name], to get information with respect to what surgical closure technique was performed for the participant.

There will be a three-week interval between the first and the second (last) testing sessions. Participants randomized to the control group will be encouraged to continue with their usual and customary exercise program. Participants in the exercise group will be instructed on performing a targeted phantom exercise program to be included in their usual and customary exercise program. At the second testing session, the same researcher will repeat all baseline measures. All data collection, including screening questionnaires and surveys of the study, will be performed through the secure REDCap platform (<https://www.project-redcap.org/>).

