Physical function assessments will be done by performing targeted phantom motor executions and four-square step test (FSST). Muscle activity will be recorded for the targeted phantom motor executions while participants are not wearing their prosthesis. However, the assessment of FSST needs participants to wear their prosthesis without EMG recording. The justification for this decision is preventing the risk of injury at the skin-prosthesis interface due to electrodes and wires. Foot plantar load will be assessed during targeted phantom motor executions and FSST. Participants will rest 2 minutes while sitting in a chair after each physical function assessment (4 minutes in total). This time will be used to instruct the participant in the testing protocol. Additional time will be provided if requested by the participant. After baseline testing is complete, EMG electrodes and sensors for the foot plantar load will be removed. Participants will then be informed of their randomization group that was determined earlier (before their baseline assessment) using the block and simple randomization techniques.

Collected data for the morphology of the residual limb, phantom phenomena, TAPES-R, PEmbS-LLA, physical function assessments, and muscle activities of the first session are baseline data and will be used for comparison to the results of the same measurements of the second session. After the first session, participants in the exercise group will be enrolled in the targeted phantom limb exercise program in addition to continuing with their usual and customary post-amputation care while participants of the control group will continue with their usual and customary post-amputation care. Participants in the exercise group will be trained on the targeted phantom limb exercise program and will have specific training sessions for three weeks at participants' homes via Zoom (<https://zoom.us/>). The researcher will make Zoom video calls to supervise participants and get assurance that all instructions are followed. After three weeks, participants of both groups will attend the test center for the second testing session. For both testing sessions, the same researcher captures the shape of the residual limb, surveys the phantom phenomena, TAPES-R, and PEmbS-LLA, assesses physical function, and conducts EMG investigations.

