#### ***Data analysis and statistics***

Different levels of comparisons will be done to explore the impact of the targeted phantom motor execution program on phantom phenomena and physical function of people with TTA. Before starting analyses, the normality of distribution of the quantitative variables will be assessed by the Shapiro-Wilk test. Since there are two groups of participants, whether participants are matched on their demographic and clinical characteristics will be explored using independent t-test and chi-square statistics. Based on our expectation of normality of distribution for the quantitative variables, if it is the case, parametric statistical tests will be used. An independent t-test will be used to compare quantitative variables within-subjects for the amputated and non-amputated sides. Similarly, Mann-Whitney test and Chi square test will be used respectively to compare ordinal and nominal categorical variables within-subjects for the amputated and non-amputated sides. An independent t-test will be analyzed to compare quantitative variables between the two groups. Similarly, Mann-Whitney test and Chi square test will be used respectively to compare ordinal and nominal categorical variables between the two groups.

Two-way analysis of variance can be used to compare the simultaneous effect of groups assignment and prosthesis embodiment on PLC. Similarly, Friedman's two-way analysis of variance will be used to compare the simultaneous effect of group assignment and surgical closure on PLC.

Spearman's correlation coefficients will be calculated to explore the potential relationship of phantom phenomena responses with participants' characteristics (i.e. age, weight, height, body mass index, length of the residual limb, the circumference of the residual limb, time after amputation, and years of prosthesis use). Moreover, the potential relationship of the phantom phenomena responses with participants' gender, type of surgery, and footedness will be explored by point-biserial correlation assessment. The potential

relationship of the phantom phenomena responses with participants' prosthesis type will be explored by partial eta square correlation assessment.

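### Nothing in the plan makes the researcher wait until after the second session to learn each participant's closure technique, although only the analysis needs it

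*Combined protocol and SAP*

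**What the plan says.** Experimental setup places the closure enquiry at the end of its account of the baseline visit: "After completion of the baseline testing, the researcher will contact" a named source "to get information with respect to what surgical closure technique was performed for the participant". The three-week interval is described next, and then the follow-up visit: "At the second testing session, the same researcher will repeat all baseline measures".

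Experimental protocol describes the coaching of the exercise arm, "The researcher will make Zoom video calls to supervise participants", and repeats the staffing of the assessments: "For both testing sessions, the same researcher captures the shape of the residual limb, surveys the phantom phenomena, TAPES-R, and PEmbS-LLA, assesses physical function".

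Data analysis and statistics uses closure as a factor, with a test to "compare the simultaneous effect of group assignment and surgical closure on PLC". It also correlates type of surgery with the phantom phenomena responses.

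The trial declares its lack of blinding: "This research is a 2-arm, parallel, open label, non-blinded randomized controlled trial". It promises no masking of closure technique.

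**The concern.** Closure technique is one of the factors whose relation to phantom control the trial wants to study. A researcher who expects one technique to preserve better control might coach those participants with more conviction, or give them more encouragement or explanation at the second session.

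The timing makes this one-sided. The enquiry follows baseline, so it cannot influence the baseline measures, whereas the coaching and session 2 may be carried out with the answer in hand. Any resulting shift would appear in session-2 values and in change from baseline, where it could be mistaken for a response to the programme that depends on closure.

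This is separate from knowledge of group. The person who coaches the exercise arm must know who is in it. That person does not need to know how the limb was closed.

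**Working it through.** The documents give no figure on this point and no arithmetic applies. The check is the order of events, and whether any step needs closure.

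**Order of events, as the text runs**

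| Step | Who | Closure obtained by enquiry? | Closure needed? |
|---|---|---|---|
| Allocation at the end of the phone interview (Experimental setup) | The researcher | No | No |
| Baseline testing (Experimental setup; Experimental protocol) | The researcher | No | No |
| Closure enquiry (Experimental setup) | The researcher | Obtained here or later | n/a |
| Zoom supervision, exercise arm only (Experimental protocol) | The researcher | Possibly | No |
| Session 2, all measures (Experimental setup; Experimental protocol) | The same researcher as at baseline | Possibly | No |
| Group and closure on PLC; type-of-surgery correlation (Data analysis and statistics) | Analysis | Yes | Yes |

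**What follows**

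1. Allocation precedes the enquiry, so closure cannot be a stratifying factor.
2. Neither the exercise programme nor any session-2 measure is said to depend on closure. The regressions draw on clinical characteristics, and closure may or may not be among them; either way, that use also comes at analysis.
3. No sentence delays the enquiry, gives it to another person, or keeps the answer from the assessor.
4. Moving the enquiry to after session 2 would therefore change no other documented step.

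**Routes by which knowing closure could act**

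- Coaching. This reaches the exercise arm only. It does not depend on who fills in the survey, because it could alter the participant's actual control.
- Administration of the phantom survey at session 2. The setup section has participants answer it on their own device or on an iPad. The protocol section has the researcher survey phantom phenomena at both sessions. The first leaves little room for influence; the second leaves some.
- Researcher-run measures (EMG, phantom motor execution, step test). These are open to influence, although electrode sites are marked and photographed for reuse. They are not the stated outcome of the closure analysis.

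**Assumptions**

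The text speaks of the researcher throughout; I take the coach to be the person who measures. I take type of surgery to mean closure technique. PLC is not spelled out in the text available here; from the survey's name I take it to be phantom limb control. The analysis section does not say whether PLC is the baseline value, the session-2 value or the change. Only the last two would be exposed.

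**The case against.** The strongest case on the other side has five parts.

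- **Timing.** A reader might infer that closure is disclosed immediately after baseline. The sentence sets an earliest time and no deadline, so a look-up after session 2 would also comply with it. Early disclosure is the natural reading, because the sentence stands between the baseline visit and the three-week interval, but it is not a rule. What stands is that the plan permits early disclosure and gives no reason for it.
- **Masking that may not exist.** A reader might infer that the enquiry destroys a masking that was otherwise intact. The documents do not show this. At baseline the same researcher examines the bare residual limb, scans it and places electrodes by muscle bulk and signal; participants may also mention their surgery. Whether any of this reveals the technique is not stated. Going to an outside source suggests that inspection is not treated as a sufficient record, so some benefit from waiting remains plausible.
- **Self-completed outcome.** If PLC comes from the participant-completed survey, direct assessor bias is limited. This stands, and leaves coaching and survey administration as the main routes.
- **Open label.** The declared lack of blinding does not oblige the researcher to learn closure early, so this part does not answer the point.
- **Larger problems remain.** Closure is not randomised, and one unblinded researcher allocates, coaches and measures. Both facts stand and would be unchanged by the fix. They limit what it achieves without making it pointless.

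A reader might also infer that the plan sets out a group-by-closure interaction that this would distort. It names a Friedman analysis of the two factors together and specifies no interaction contrast.

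**Conclusion.** The point holds as a minor, good-practice matter. The plan has the researcher obtain closure technique after baseline without waiting for session 2. The researcher then coaches the exercise arm, and the same researcher runs session 2. No documented step before analysis needs the information.

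The size of any bias cannot be known from the documents. An inflated false-positive rate could be calculated only by supplying both a bias and a number of participants per closure type; the text available here gives neither, so no rate is offered. The direction is also unknown, since it depends on what the researcher expects.

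The conclusion rests on the coach and the assessor being the same person, on closure not already being evident to that person in every participant, and on the closure analysis using session-2 or change values. If limb examination always reveals the technique, or if only baseline PLC is analysed, the point has no practical force.

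**What to change.** Change the sentence in Experimental setup so that closure technique is requested after the participant's second testing session, or in one batch after the last participant's second session. The batch version is slightly stronger, because the researcher then cannot build expectations about closure from earlier participants' known techniques and results.

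The cost is a change of timing, with no added procedure or staff. The small downside is less time to chase a missing record.

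The change does not deal with confounding in the closure comparison or with the researcher's knowledge of group. Any report of the closure results should still state both, and should say whether the technique was evident from examination or from the participant.

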### ***Experimental protocol***

At the beginning of the baseline testing session, the researcher measures participants' weight and height using a scale and stadiometer; the body mass index will be calculated using REDCap programmed formula. Then the researcher will survey prosthetic embodiment by asking participants to fill out the revised version of the Trinity Amputation and Prosthesis Experience Scales (TAPES-R) and Prosthesis Embodiment Scale for Lower Limb Amputees (PEmbS-LLA), which are brief self-administered questionnaires to assess the adjustment and interaction of people with amputation to their prosthesis. Then, the researcher will ask participants to sit on a chair within parallel bars and remove their prosthesis. The researcher will examine the residual limb and places paper skin markers on specific landmarks over their residual limb (i.e. middle of the patella, tibial tuberosity, the distal end of the residual limb). Then, participants will stand securely inside parallel bars while the researcher captures the shape of their residual limb using a 3D scanner (OMEGA Scanner 3D, Willow Wood, Ohio, USA). The morphologic characteristics of the residual limb (i.e. length, circumference, and volume) will be recorded. If the participant finds it difficult to stand without the prosthesis, the scan will be performed in sitting and note in the assessment. The participant will then return to the sitting position and placement for the electromyography (EMG) electrodes (Trigno, Delsys Inc., Massachusetts, USA) will be determined on both the intact and amputated limbs based on the standard electrode placement guideline. However, for the amputated side, since the length of the muscles has changed, the location of the EMG electrodes needs to be determined specifically for each participant based on the new muscle bulk and optimal electrical signal activity. Electromyography of the tibialis anterior, medial and lateral heads of the gastrocnemius muscle will be recorded for both sides. Electrode locations will be marked and photographed to ensure consistency with subsequent testing session recordings. The skin will be cleaned using an alcohol pad and electrodes will be attached using paper tape.

Physical function assessments will be done by performing targeted phantom motor executions and four-square step test (FSST). Muscle activity will be recorded for the targeted phantom motor executions while participants are not wearing their prosthesis. However, the assessment of FSST needs participants to wear their prosthesis without EMG recording. The justification for this decision is preventing the risk of injury at the skin-prosthesis interface due to electrodes and wires. Foot plantar load will be assessed during targeted phantom motor executions and FSST. Participants will rest 2 minutes while sitting in a chair after each physical function assessment (4 minutes in total). This time will be used to instruct the participant in the testing protocol. Additional time will be provided if requested by the participant. After baseline testing is complete, EMG electrodes and sensors for the foot plantar load will be removed. Participants will then be informed of their randomization group that was determined earlier (before their baseline assessment) using the block and simple randomization techniques.

Collected data for the morphology of the residual limb, phantom phenomena, TAPES-R, PEmbS-LLA, physical function assessments, and muscle activities of the first session are baseline data and will be used for comparison to the results of the same measurements of the second session. After the first session, participants in the exercise group will be enrolled in the targeted phantom limb exercise program in addition to continuing with their usual and customary post-amputation care while participants of the control group will continue with their usual and customary post-amputation care. Participants in the exercise group will be trained on the targeted phantom limb exercise program and will have specific training sessions for three weeks at participants' homes via Zoom (<https://zoom.us/>). The researcher will make Zoom video calls to supervise participants and get assurance that all instructions are followed. After three weeks, participants of both groups will attend the test center for the second testing session. For both testing sessions, the same researcher captures the shape of the residual limb, surveys the phantom phenomena, TAPES-R, and PEmbS-LLA, assesses physical function, and conducts EMG investigations.

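### Groups are assigned by phone before signed consent and baseline testing, with no concealment described, so the baseline tester may know the arm

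*Combined protocol and SAP*

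**What the plan says.** Under Experimental setup, the first contact is by telephone: "obtaining verbal consent to participate, and gathering screening information will be done via phone interview". Assignment follows in the same call: "At the conclusion of the phone interview, the researcher will randomly assign participants to the control or exercise groups". Written consent is taken later, in person: "The baseline visit will begin with review of expectations and the participant will sign informed consent".

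The Experimental protocol section confirms the order. After describing the end of baseline testing it states: "Participants will then be informed of their randomization group that was determined earlier (before their baseline assessment) using the block and simple randomization techniques". Participants therefore learn their group only after baseline testing, although the group already exists.

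The term used for the person who allocates is also used for the person who tests at baseline and for the person who supervises the exercise arm by video call. One and the same researcher does both testing sessions. The trial is described as open label and not blinded.

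Nothing in the baseline visit depends on the arm: "The baseline testing session will be entirely the same for participants of both groups".

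**The concern.** An open-label trial cannot blind treatment, but it can protect everything that happens before the arm exists. This plan gives up that protection without a stated reason. Three things follow.

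- **Arm-aware baseline testing.** If the tester knows the arm, steps that rest on the tester's judgement are exposed: placing limb landmarks, instructing and running the function tests, and siting electrodes on the amputated side, where the location "needs to be determined specifically for each participant based on the new muscle bulk and optimal electrical signal activity". TAPES-R and PEmbS-LLA are less exposed. They are self-administered, and participants do not yet know their group. The same applies to the phantom limb survey where it is completed online or on a tablet.
- **Loss after randomization.** Anyone who drops out between the call and the visit, or declines to sign, is already randomized with no in-person baseline data. The available text does not say how such people are counted. The losses would differ by arm only if the researcher acted on the allocation or disclosed it.
- **Unclear scheme.** Block randomization and simple randomization are different methods. The text names both, without a block size or a word on how they combine. This is a side issue and the timing argument does not depend on it.

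A distortion confined to baseline enters any between-group comparison of change. The Experimental protocol section says that first-session data will be compared with the second session. The Data analysis and statistics section does not say whether the between-group t-test uses change or follow-up values.

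**Working it through.** **Order of events**

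1. Telephone screening and verbal consent (Experimental setup).
2. Assignment by the researcher at the end of the call (Experimental setup).
3. Signed consent at the start of the in-person visit (Experimental setup).
4. Baseline testing by the researcher (Experimental setup and Experimental protocol).
5. Participant told the group (Experimental protocol).

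The two sections agree, so the early allocation is a stated rule and not a slip of wording. REDCap is named for data collection only ("All data collection, including screening questionnaires and surveys of the study, will be performed through the secure REDCap platform"), not for allocation. No independent list holder and no arm-unaware tester is mentioned.

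**Size, as an illustration**

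The plan gives no figure on this point to reproduce. The available text has no sample size, SD, correlation or assessor effect. The only input from the plan is the 0.05 significance level, taken here as two-sided. Assumed inputs:

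- n = 10, 20 or 30 per arm;
- correlation between baseline and follow-up ρ = 0.5, 0.7 or 0.9;
- outcome SD 1 at each session;
- a shift δ = 0.1 or 0.2 SD in one arm's baseline only, with no true treatment effect.

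The rejection rate comes from the noncentral t distribution with noncentrality bias / (SD × √(2/n)):

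- Change score: bias = δ, SD = √(2(1 − ρ)), df = 2n − 2.
- ANCOVA (not named in the plan): bias = ρδ, SD = √(1 − ρ²), df = 2n − 3.
- Follow-up only: bias = 0.

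Middle case, n = 20, ρ = 0.7, δ = 0.2, so √(2/20) = 0.316:

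- Change score: SD = √0.6 = 0.775; noncentrality = 0.2 / (0.775 × 0.316) = 0.82; type I error 12.5%.
- ANCOVA: bias = 0.14, SD = √0.51 = 0.714; noncentrality = 0.14 / (0.714 × 0.316) = 0.62; type I error 9.3%.

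| Shift in one arm's baseline | Test | Middle case | Range over n and ρ |
|---|---|---|---|
| 0.1 SD | change score | 6.8% | 5.5% to 13.6% |
| 0.1 SD | ANCOVA | 6.1% | 5.2% to 12.3% |
| 0.2 SD | change score | 12.5% | 7.1% to 39.9% |
| 0.2 SD | ANCOVA | 9.3% | 5.7% to 34.9% |
| either | follow-up only | 5.0% | 5.0% |

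A simulation with 40,000 replicates gave 12.7%, 9.4% and 5.0% (change, ANCOVA, follow-up only) for n = 20, ρ = 0.7, δ = 0.2. For n = 30, ρ = 0.9, δ = 0.2 it gave 40.0% (change) and 34.1% (ANCOVA).

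**Electrode siting behaves differently.** The plan says: "Electrode locations will be marked and photographed to ensure consistency with subsequent testing session recordings". A siting effect would therefore tend to carry into both sessions. If a 0.2 SD shift is carried over in full, the change score has bias 0 and stays at 5.0%. A follow-up-only test has bias 0.2 and SD 1, which gives 7.1%, 9.5% and 11.9% at n = 10, 20 and 30.

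**The case against.** The strongest reply is that the harm is a chain of conditions. The tester must know the arm, must distort baseline in one direction, and that distortion must reach the comparison actually used. The plan also limits the room for it. Participants are not told their group until baseline testing is over, the session is identical for both groups, limb shape comes from a 3D scanner, and electrode siting starts from a standard guideline. The most concrete example, electrode siting, largely cancels in change because sites are photographed for reuse. Every input to the calculation is assumed, and the highest figures need 30 per arm, a correlation of 0.9 and a 0.2 SD shift together. The opening part of the document was not available, so concealment may be described there. The same researcher still tests at follow-up in an open-label trial, which may be the larger source of assessor bias.

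Much of this stands. It means that the size of the bias is unknown and that the upper ends of the ranges are corner cases. It does not answer the point about order. Withholding the group from participants protects their responses but leaves the researcher uncovered. Concealment described elsewhere would still leave assignment ahead of signed consent and baseline. Since the plan does not say whether change or follow-up values are compared, neither route to bias can be ruled out. Unblinded follow-up is a separate limitation and no reason to leave baseline unprotected.

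**Conclusion.** The concern holds. It is certain from the text that allocation precedes signed consent and all in-person baseline testing, and that the available text describes no concealment. That the baseline tester knows the arm is a reasonable inference from the shared role term, not a stated fact.

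The effect on results cannot be sized from the documents. Under the assumptions above, the middle case gives a type I error of 6.1% to 12.5% for analyses that use baseline, against a nominal 5%. For a follow-up-only test there is no inflation if the shift is confined to baseline, and 9.5% at 20 per arm if a 0.2 SD siting effect is carried into both sessions. Selection and loss before the visit were not quantified.

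This is a change that should be made: the likely harm is uncertain, but it is cheap to prevent and no reason is given for the present order.

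**What to change.** - **Experimental setup:** remove assignment at the end of the telephone call. State that assignment takes place at the baseline visit, after consent is signed and all baseline measures are saved in REDCap.
- **Experimental protocol:** replace the statement that the group was fixed before baseline with one saying that it is generated and revealed at that point, from a pre-loaded concealed list released through the existing REDCap project. Say who prepares and holds the list; this should be someone who does not enrol, test or train participants, since a list loaded by the tester is not concealed.
- **Scheme:** name one method, for example permuted blocks of randomly varying size, and delete the reference to simple randomization.
- **Limitation:** state that this does not remove unblinded assessment at follow-up.

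The cost is two wording changes, setting up the list, and confirming that the REDCap project can release allocations, because the plan names it only for data collection. No extra visit is needed. The downside is that the arm is unknown until the end of the baseline visit, so exercise sessions can be scheduled only then.

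### One role allocates, supervises the exercise arm and assesses both sessions unmasked; part of the observer, interviewer and processing bias can be reduced without an extra in-person assessor

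*Combined protocol and SAP*

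**What the plan says.** Experimental setup declares a "2-arm, parallel, open label, non-blinded randomized controlled trial". Allocation comes early and is made by the researcher: "At the conclusion of the phone interview, the researcher will randomly assign participants to the control or exercise groups". Participants hear the result only once baseline testing is over: "Participants will then be informed of their randomization group that was determined earlier (before their baseline assessment".

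During the three weeks between sessions the exercise arm has supervised contact: "The researcher will make Zoom video calls to supervise participants and get assurance that all instructions are followed". No comparable contact with controls is described.

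At the end of that interval, "At the second testing session, the same researcher will repeat all baseline measures". Experimental protocol repeats this and lists the measures: "For both testing sessions, the same researcher captures the shape of the residual limb, surveys the phantom phenomena, TAPES-R, and PEmbS-LLA, assesses physical function", together with the EMG work.

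On questionnaires, Experimental setup provides a remote route for the phantom survey before baseline ("The participant will be e-mailed a link to complete the following surveys/questionnaires"), with an iPad at the clinic for those who have not finished. Experimental protocol says of TAPES-R and PEmbS-LLA, "which are brief self-administered questionnaires". All data collection runs through REDCap.

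**The concern.** An exercise program cannot be hidden from participants, so an open-label design is understandable. It does not follow that assessment and data processing must also be open. As written, a participant in the exercise arm meets at session 2 the role that coached them for three weeks. That role oversees the questionnaires, gives the FSST instructions and runs the recordings. Nothing in the available text says that arm or session is hidden when the recordings are turned into numbers.

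Three sources of bias follow: answers shaped by the presence of the trainer, instructions or encouragement that differ by arm, and processing decisions made with the arm known. Each could plausibly favour exercise, although the documents neither establish the direction nor give a size. Because the researcher allocates before the baseline visit, the baseline measures are also taken with the arm known, so change from baseline is exposed at both ends.

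**Working it through.** **Step 1: who does what.**

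| Task | Role named | Where |
|---|---|---|
| Allocation, before baseline | the researcher | Experimental setup |
| Zoom supervision, exercise arm | the researcher | Experimental protocol |
| All measures, both sessions | the same researcher | Experimental setup; Experimental protocol |
| Masked processing or analysis | not described in the available text | – |

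The phrase about the same researcher literally links only the two testing sessions. That the trainer is also the assessor is inferred from the consistent singular.

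**Step 2: where knowledge of the arm can enter, and what a procedural change can reach.**

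| Outcome | How it is obtained | Reachable | Not reachable |
|---|---|---|---|
| Phantom survey, TAPES-R, PEmbS-LLA | Participant answers; data in REDCap | Influence of the researcher's presence and prior talk | Participant's own expectation |
| FSST | Instructed and assessed in person | Wording of instructions | Effort and encouragement |
| EMG | Recorded; amputated-side electrode sites chosen individually | Processing of the file | Site choice (sites are marked and photographed, which helps consistency but does not mask) |
| Scan | Recorded after skin markers are placed by hand | Processing of the file | Marker placement |
| Plantar load | Recorded | Processing of the file | Effort and encouragement |

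Each outcome has a part that can be reached and a part that cannot. The documents do not say how the bias divides between them.

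**Step 3: illustration of what is at stake.** The plan gives no figure on this point to reproduce. The significance threshold of 0.05 and the independent t-test for quantitative between-group comparisons come from Data analysis and statistics. Everything else is assumed: a two-sided test (sidedness is not stated), *n* per arm (no sample size appears in the available text), and a between-arm bias of *b* SD with no true effect.

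Formula: degrees of freedom 2*n* − 2; noncentrality δ = *b* × √(*n*/2); rejection rate = P(|T| > critical value), where T is noncentral t with parameter δ.

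- *n* = 20: √10 = 3.162, 38 degrees of freedom.
  - *b* = 0.2: δ = 0.632, rate 0.095
  - *b* = 0.3: δ = 0.949, rate 0.152
  - *b* = 0.5: δ = 1.581, rate 0.338
- *n* = 30: √15 = 3.873, 58 degrees of freedom.
  - *b* = 0.2: δ = 0.775, rate 0.119
  - *b* = 0.3: δ = 1.162, rate 0.208
  - *b* = 0.5: δ = 1.936, rate 0.478

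The nominal rate is 0.05. For a fixed bias the error grows with *n*, so recruiting more participants does not help. At 20 per arm, reducing an assumed bias from 0.5 to 0.2 SD would lower the error from 0.338 to 0.095. This shows that partial reduction would be useful; it does not show that the changes below achieve it. The figures also do not cover the ordinal and nominal outcomes, which are to be tested by Mann-Whitney and chi-square.

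**The case against.** The strongest reply is that open label is a declared design choice and that much of the remedy is already in place: self-administered scales, REDCap throughout, instrument recordings and photographed electrode sites. Most of this stands. The plan does not contradict itself here, and the point is an improvement to it. What the plan leaves open is whether session-2 questionnaires are completed unaided and before any talk about training, and whether files are processed without knowledge of the arm.

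A reader might infer stronger claims that the documents do not support:

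- **That survey mode changes from self-completion at baseline to interview at session 2.** The sentence on surveying covers both sessions. Experimental protocol describes surveying embodiment as asking participants to fill out the scales, and session 2 is to repeat the baseline measures. Nothing says that items are read aloud.
- **That the researcher measures every outcome.** TAPES-R and PEmbS-LLA are answered by the participant. The accurate wording is that the researcher administers or measures the outcomes.
- **That masked processing would deal with landmarks and electrodes.** Both are placed on the limb before any file exists.

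A fair practical objection is that whoever recorded the files cannot easily mask themselves. That stands: the code key must be kept away from the person doing the processing, and this belongs in the cost.

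**Conclusion.** The concern holds in a limited form. The role that allocates and supervises the exercise arm also, on the natural reading, administers or measures all outcomes at both sessions knowing the arm, and no masked processing is described in the available text. Part of the observer, interviewer and processing bias can be reduced without an extra in-person assessor.

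It may be tempting to conclude that most of the bias can be removed this way. The documents give no size for the bias and no split between observer and participant shares, and phantom phenomena and embodiment are reported by participants who know their group. The size of the reduction is therefore undetermined.

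The false-positive rates (9.5% to 34% at 20 per arm, 12% to 48% at 30 per arm) rest on assumed shifts of 0.2 to 0.5 SD and assumed sample sizes. They illustrate what a bias of that total size would do. They do not estimate the bias in this trial. The change is worth making because it is cheap.

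**What to change.** 1. In Experimental protocol, state that at session 2 participants complete the phantom survey, TAPES-R and PEmbS-LLA unaided in REDCap, in the same mode as at baseline and before any discussion of training.
2. Have an automated script assign random codes to the EMG, plantar-load and scan files so that arm and session are hidden. Fix the processing settings in advance, and unmask only after the derived values are locked.
3. Use scripted FSST instructions, identical for both arms and both sessions.
4. State as limitations what these steps leave untouched: participant expectation, unequal researcher contact between arms, encouragement during testing, and unmasked landmark and electrode placement.

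Cost: protocol wording, a file-coding step with the key held away from the processor, and slightly slower processing. No extra in-person assessor or visit is needed.
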